Engaging Medically Complex Veterans in Tele-Rehabilitation Using a Biobehavioral Approach: A Pilot Study of Feasibility and Acceptability

NCT04942613

July 14, 2022

COMIRB Protocol

COLORADO MULTIPLE INSTITUTIONAL REVIEW BOARD
[name] [contact] [contact]

Protocol #: 21-2773

Project Title: Engaging Medically Complex Veterans in Tele-Rehabilitation Using a Biobehavioral Approach: A Pilot Study of Feasibility and Acceptability

Principal Investigator: [name] [name]

Version Date: 07.14.2022

I. Hypotheses and Specific Aims:

This is a single-site, randomized pilot study using a two-group (GROUP1 and GROUP2) crossover design. Fifty Veterans with medical complexity and deficits in physical function will participate. Outcomes will be assessed at baseline (pre-intervention), 6 weeks (intervention mid-point), 12 weeks (end of intervention), and 24 weeks.

AIM 1: To determine the feasibility and acceptability of a multicomponent telerehabilitation program.

Hypothesis 1a: 75% of Veterans will achieve $\geq 80\%$ adherence as measured by attendance.

Hypothesis 1b: At least 75% of Veterans will perceive the program as acceptable ($\geq 4/5$ on Acceptability of Intervention Measure¹³) and feasible ($\geq 4/5$ on Feasibility of Intervention Measure). In addition, we will monitor adverse events and categorize severity (mild, moderate, severe) and relatedness (definitely, probably, possibly).

AIM 2: To assess the preliminary response of a multicomponent telerehabilitation using a two-group randomized crossover design and determine variability estimates. Outcomes for this aim are accelerometer-based physical activity, physical function, quality of life, and loneliness.

Hypothesis 2: At program end (GROUP1 12 weeks, GROUP2 24 weeks), participants will have a trend of improved outcomes (accelerometer 7-day average step count with ActiGraph physical activity monitors (ActiGraph Inc. Pensacola FL, primary) compared to program start (GROUP1 baseline, GROUP2 12 weeks). In addition, using the pooled intervention sample, variability estimates (standard deviation), will be determined for change in physical activity, physical function (,30 second sit to stand¹⁴) and self-report measures of physical function (Activity Measure for Post-Acute Care¹⁵), quality of life (PROMIS 29 Profile v2.0¹⁶), and loneliness (3-item loneliness scale¹⁷ Berkman Social Disengagement Scale¹). This will allow for sample size estimates for the subsequent larger effectiveness trial.

AIM 3 (exploratory): Explore patient perspectives of the multicomponent telerehabilitation program (physical therapy, biobehavioral interventions, technology, and social support interventions) and how they contribute to program engagement and participation as well as changes in physical activity.

Objective 3a: Qualitatively identify factors Veterans associate with program engagement and participation as well as short-term changes in physical activity (immediately post 24-week outcome assessment); these data will deepen our understanding of how and why Veterans engage with the program and its components and identify targets for future interventions.

Objective 3b: Qualitatively identify factors Veterans associate with maintenance of physical activity up to 6 months after program completion, with an emphasis on social support, strategies learned from biobehavioral interventions, and technology. These data will help identify key factors related to maintenance of physical activity, inform future iterations of this multicomponent program, and identify targets for future interventions.

II. Background and Significance:

A.1. Older Veterans with complex health conditions are often excluded from rehabilitation research

Veterans with multiple comorbidities are one of the most vulnerable patient populations as well as a large and growing proportion of Veterans Health Administration (VHA) beneficiaries.¹⁸ Older Veterans with complex health conditions are at high risk for isolation,¹⁹ disability,²⁰ adverse health events (e.g., hospitalization and death), mental illness,²¹ and heavy healthcare utilization.²⁰ Historically, musculoskeletal research has often excluded medically complex older adults, which has hindered development and evaluation of practical and effective rehabilitation strategies for this population. The reason for this selection bias is multifaceted. The population is heterogeneous in age, cognitive status, medical status, psychological comorbidity, living environment, and social support.²² In addition, this at-risk population often experiences simultaneous acute and chronic conditions that contribute to variability in rehabilitation outcomes and high rates of loss to clinical follow-up. Ethical considerations also create additional barriers to research participation, as many older Veterans have cognitive impairments that impact the informed consent process.²³ However, such selection bias limits the generalizability of study findings and the likelihood that existing or new interventions will adequately address the needs of this growing population.²² Therefore, rehabilitation research targeting medically complex older Veterans is needed to optimize their physical function and enhance their life participation.

A.2. Physical function is a powerful biomarker of health and clinical outcomes for older adults

Although disability risk factors are complex and multifactorial, there is evidence that physical function alone is a powerful biomarker of overall health following hospitalization, and a strong independent predictor of hospital re-admission.²⁴⁻²⁷ Poor physical function is also associated with reduced walking ability, lower extremity weakness, and increased risk of falls.^{24,28-31} Older adults with lower levels of physical activity at home are approximately 6 times more likely to be readmitted within 30 days of acute hospitalization than those with higher levels of physical activity.²⁴ Furthermore, objective lower extremity weakness is associated with increased likelihood of requiring assistance at home.³² This

evidence highlights the need for intensive and multimodal interventions directly addressing factors that contribute to low physical function and physical activity in this population. Most importantly, physical function is a modifiable risk factor, even in medically complex older adults, which previous studies suggest can be effectively addressed with more intensive rehabilitation strategies.

A.3. Social isolation of older Veterans is associated with poor physical function

Social isolation is also associated with poor physical function,³³ and is predictive of rehospitalization, premature death, and poor health outcomes³⁴ in older Veterans. Active older adults perceive social support and connectivity as important motivators for exercise.^{11,12} In studies of healthier populations the social connection provided by group exercise also boosts adherence,³⁵ increasing long-term sustainability of exercise benefits.

However, older Veterans with poor health status have geographic (e.g., rural) and physical barriers to rehabilitation participation and often experience greater social isolation. The use of technology, such as telehealth platforms, provides an avenue to address the problem of Veteran social isolation. While online social activity is a detriment to perceived health for young adults, older adults report feeling more social support and less isolation when connected online.³⁶ Increasing Veteran social connectivity may augment conventional rehabilitation to improve older Veterans' physical activity, life participation, and sustained outcomes.

A.4. Conventional Rehabilitation Strategies are Insufficient to Produce Meaningful Gains

We have found rehabilitation exercise dosage in a variety of settings often does not provide a meaningful physical challenge for older adults.⁶ Across the U.S., the content and intensity of conventional rehabilitation for medically complex older adults is substantially under-dosed.³⁷⁻³⁹ In the rare cases where resistance training is used, the loads are often equivalent to 2 pounds or less. This is not sufficient to induce physiologic adaptations.⁴⁰ In contrast, high-intensity resistance training tailored to individual patient tolerance integrates principles of physiologic tissue overload and resistance training into functional rehabilitation interventions to achieve better outcomes. Despite this, clinicians apply conservative interventions to medically complex populations because they fear patient injury or expect patients to resist working at higher intensities.^{41,42} Yet, when employed correctly, there is no greater risk of injury or patient refusals.^{43,44} In older adults, high-resistance, low repetition strengthening fosters better functional outcomes than traditional strength training, including greater gains in strength^{45,46} and physical function.⁴⁷ Furthermore, data from our group suggests practice change from low-intensity to high-intensity functional resistance interventions is influenced by patient and clinician self-efficacy,⁴⁸ which are modifiable through enhanced patient engagement and enriched training for rehabilitation clinicians. Furthermore, improvements in physical function are sustained well beyond a discrete episode of care,⁴³ helping to protect against the decline that might occur with the next expected insult.

III. Preliminary Studies/Progress Report:

B.1.1. Clinical Research Experience

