Aim 3: Qualitative data will be collected primarily through semi-structured one-on-one key informant interviews, which will be recorded with the participant's permission. All interviews will be conducted through the same virtual platform participants will have been using throughout program participation. To validate data and findings, additional qualitative data will be collected from documentation in CPRS (restricted to study-related documentation) and voluntary feedback provided through the veteran satisfaction survey (V signals—a validated survey instrument used routinely within the VA). Objective 3a: These interviews will be conducted within 3 weeks of program completion (12-weeks for participants in Group1 and 24 weeks for participants in Group2). The interviews will last approximately 45-60 minutes. We will purposively sample Veterans based on level of technology engagement [high engagers (respond to Annie \geq 80%) versus low engagers (respond to Annie $<$ 50%)] and group sessions attendance [high attendance (\geq 80%) versus low attendance ($<$ 50%)]. We will continue to sample Veterans until thematic saturation is reached for each group. Objective 3b: We will conduct follow-up interviews with the Veterans who completed initial interviews (from objective 3a); these interviews will last approximately 30-45 minutes and will occur between 3 to 6 months following their initial interview.

Description of Population to be Enrolled:

In this study, the target population is older Veterans, including those identified as "high-need, high-risk" by the Geriatrics & Extended Care Data & Analysis Center (GECDAC); this designation includes Veterans who have experienced a significant health event in the last 12 months (e.g., hospitalization) and have a Frailty Index score \geq 6. Veterans will be recruited through the VA Eastern Colorado Health Care System. Potential Veterans will be identified by the GECDAC and/or by providers in the Geriatric Specialty Clinic, Home

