Based Primary Care, and inpatient and outpatient rehabilitation settings. Potential Veterans with whom we have a treatment relationship will be pre-screened through standardized chart review followed by standardized phone screen. If eligible and interested in participating, Veterans will provide informed consent and be enrolled in the study; once enrolled, they will be randomized to either a waitlist control (GROUP2) or experimental (GROUP1) group. Participants will complete surveys and direct observation (Aims 1 & 2). Veterans will also undergo performance-based assessments of physical activity and physical function and complete self-reported measures for physical function, quality of life, loneliness, social support, and mental health.

Formal Inclusion/Exclusion Criteria

Inclusion

- ≥ 60 years of age
- Multiple chronic conditions (Functional Comorbidity Index⁶⁸ ≥ 3)
- Impaired physical function (≤ 10 on 30 second sit to stand)

Exclusion

- Life expectancy < 12 months
- Acute or progressive neurological disorder (e.g., Amyotrophic Lateral Sclerosis, recent stroke)
- Moderate to severe dementia without caregiver assistance (< 18 on telephone Montreal Cognitive Assessment (T-MoCA)⁶⁹)
- Unstable medical condition precluding safe participation in progressive rehabilitation (e.g., unstable angina) as defined by ACSM guidelines

We plan to randomize 50 Veterans (25 randomized to each group), with the goal of having 40 Veterans complete the study (20% attrition rate). Due to our enrollment process, we plan to have 70 Veterans sign the informed consent; this will allow for up to 20 Veterans to complete evaluation but be found ineligible based on identified exclusion criteria. The goal of the study is to obtain a representative sample of older Veterans at risk for, or presenting with, impaired physical function contributing to fall risk, physical dependence, and risk for hospitalization. Both sexes and all races are included in the study, however the Veteran population is predominantly male and Caucasian, which will be reflected in the enrollment.

D. Study Design and Research Methods

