We propose a pilot, two-arm randomized trial using a waitlist control to determine the feasibility, acceptability, and safety (AIM 1) of a 12-week multicomponent telerehabilitation program. We will also assess the preliminary response (AIM 2) to this 12-week intervention. Participants (n=50) will be randomized to GROUP1 or GROUP2 using computer-generated random blocks of 2 and 4, stratified by sex. A waitlist control (GROUP2) will be used to simultaneously achieve the aims and ensure that all participants receive the intervention. Data will be collected at baseline (pre-intervention),

6-weeks (intervention midpoint for GROUP1), 12 weeks (intervention end for GROUP1, primary endpoint), and 24 weeks.

Setting & Recruitment:

Following consent and prior to baseline assessment and randomization, each participant will complete a physical therapy evaluation performed by a licensed physical therapist. The purpose of this evaluation is to ensure the Veteran is appropriate for the planned intervention and is eligible for the study. The evaluation may include standard evaluation tasks including but not limited to chart review, subjective history, and functional assessment.

Initial evaluation, intervention, and testing will occur through telehealth via VA Video Connect using a site-to-home format. Dedicated telehealth rooms are available for the study team in the ECHCS GRECC. Veterans will have the option of using their personal device (e.g., tablet, computer) or a VHA-issued tablet.

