Heterogeneity of medically complex older adults: Medically complex older adults are heterogeneous in age, cognitive status, medical status, psychological comorbidity, living environment, and social support.²² Additionally, they experience acute exacerbations of chronic conditions impacting their response to treatment and contributing to high drop-out rates among this population. To accommodate for this from our experiences, we anticipated a higher attrition rate (20%) and adjusted enrollment accordingly.

G. Data Analysis Plan:

Analysis Plan. Analyses will be performed in SAS v 9.4 or above and hypothesis tests will be two-sided, assuming an alpha level of 0.05. Participant characteristics and outcome variables will be summarized using means, standard deviations (SD), medians, ranges, N and percent, as appropriate.

Aim 1. The percent of Veterans (1) achieving $\geq 80\%$ adherence and (2) scoring $\geq 4/5$ on the Acceptability of Intervention Measure will be calculated with associated 95% exact binomial confidence intervals. We will additionally calculate the proportion of adverse events that are found to be possibly, probably, or definitely related to the intervention.

Aim 2. Given the small samples, the median change from baseline to 12 weeks for those randomized to the intervention will be compared between the groups using a Wilcoxon rank-sum test for each outcome of interest (7-day average step count as primary). Estimates of variability (SD) in the change from pre to post-intervention for the pooled sample completing the intervention (N=40) will be calculated for each outcome and reported with 95% CIs. These estimates and the CIs will inform sample size calculations for a future effectiveness trial.

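### Hypothesis 2 is an uncontrolled before-after statement that does not match the randomised week-12 comparison in Section G, and nothing says which one decides Aim 2

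*Combined protocol and SAP*

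**What the plan says.** Three parts of the combined protocol and SAP bear on how Aim 2 is judged.

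- **Section I, Hypothesis 2.** At the end of the program (week 12 in GROUP1, week 24 in GROUP2), "participants will have a trend of improved outcomes", with the reference point given as "compared to program start (GROUP1 baseline, GROUP2 12 weeks". Each participant is compared with their own program start. GROUP1 contributes weeks 0 to 12 and GROUP2 weeks 12 to 24. The word trend is not defined. Pooling is explicit only for the SDs: "using the pooled intervention sample, variability estimates (standard deviation), will be determined".
- **Section D.** The design is a two-arm randomised trial with a waitlist control, 25 per group. The time points include "12 weeks (intervention end for GROUP1, primary endpoint".
- **Section G, Aim 2.** The median change from baseline to 12 weeks is "compared between the groups using a Wilcoxon rank-sum test for each outcome of interest", with step count primary and two-sided tests at 0.05. The pooled completers (N=40) are used only to estimate the SD of change.

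For the primary outcome, the ActiGraph paragraph at the end of the outcomes text in Section D lists wear at baseline and week 12 for GROUP1, and at weeks 12 and 24 for GROUP2. Sections I and D say in general terms that outcomes are collected at baseline.

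**The concern.** The waitlist group is what allows program response to be told apart from change that would have happened anyway. Hypothesis 2 does not use it. GROUP1 has no control period, so putting both groups' start-to-end changes together cannot remove time effects. Section G does use the control, but for a contrast that no hypothesis states. If the two disagree, for example a clear before-after gain with no difference between groups, the plan does not say which is the Aim 2 result. Section H says that response will be measured to judge preliminary effectiveness, so the choice affects how the pilot is read.

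The wear schedule adds to this. Taken literally, GROUP2 has no step-count change from baseline to week 12. For the primary outcome, only the uncontrolled contrast could then be computed as a change.

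**Working it through.** **The plan's own figure.** 40 completers at 20% attrition needs 40/(1 − 0.20) = 50 randomised, as stated; 70 consented − 20 ineligible = 50 agrees. The documents give no effect size, SD of change or power for Aim 2, so there is nothing further to reproduce.

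**What each contrast estimates.** Let *e* be the program effect, *d1* the natural drift over weeks 0 to 12, and *d2* the drift over weeks 12 to 24, all in SDs of 12-week change.

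- Start-to-end change with equal group sizes: *e* + (*d1* + *d2*)/2.
- Randomised change to week 12: (*e* + *d1*) − *d1* = *e*.

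**Inputs.** From the documents: 40 completers, taken as 20 per group, and two-sided alpha 0.05. Assumed: normal changes with SD 1, the same drift *d* in every 12-week period, *e* = 0, and *d* from 0 to 0.5.

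**Formulas.**

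- Chance of a positive mean change, n = 40: Φ(*d*√40). At *d* = 0.2 this is Φ(1.265) = 0.897.
- Chance of a significant improvement: the upper tail of a noncentral t with 39 df and noncentrality *d*√40, beyond the 97.5% point of t with 39 df. A simulated signed-rank test checks it.
- Randomised contrast: simulated Wilcoxon rank-sum, 20 against 20, significant in favour of the program.

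| Drift *d* (assumed) | Positive mean, n = 40 | Significant improvement, paired t | Significant improvement, signed-rank | Rank-sum favours program |
|---|---|---|---|---|
| 0 | 50% | 2.5% | 2.2% | 2.5% |
| 0.1 | 74% | 9.0% | 8.8% | 2.4% |
| 0.2 | 90% | 23.4% | 21.8% | 2.5% |
| 0.3 | 97% | 45.6% | 43.6% | 2.6% |
| 0.5 | 99.9% | 86.9% | 86.0% | 2.5% |

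**Downward drift.** With *e* = 0.3 and *d1* = *d2* = −0.3, the expected start-to-end change is 0.3 − 0.3 = 0, so a real response would look like none. The randomised contrast would still estimate 0.3.

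**Precision of the randomised contrast.** The 95% CI half-width for a mean difference is 2.024 × √(2/20) = 0.64 SD. Simulated rank-sum power is about 32% at 0.5 SD, 67% at 0.8 SD and 85% at 1.0 SD.

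**The case against.** The strongest reply is that control is already planned. The only Aim 2 test in Section G is between groups, week 12 is the primary endpoint, and Section G uses the pooled sample for SDs alone. This is also a feasibility pilot, which needs no powered test. All of that stands. It makes the defect one of alignment between hypothesis and analysis, but it does not supply the missing statement of which one decides.

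Several stronger readings are tempting, and the documents do not support them.

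- *Aim 2 will be concluded from recovery alone.* No section says so, and Section H does not tie preliminary effectiveness to the before-after change.
- *Participants are enrolled at a low point, so drift must be upward.* The target population includes "Veterans who have experienced a significant health event in the last 12 months", but the formal criteria do not require such an event, and recruitment also uses flyers, websites and record review. Section G's preceding text on heterogeneity (Section F) mentions acute exacerbations, so decline is equally possible.
- *Selection on sit to stand inflates that outcome by a known amount.* Entry requires "Impaired physical function (≤ 10 on 30 second sit to stand", and the same test is an outcome. With SD 4, source mean 10 to 12 and retest correlation 0.7 to 0.9 (all assumed), regression to the mean would add about 0.3 to 1.4 stands in GROUP1 if the qualifying test were also the baseline. Section D places the eligibility evaluation before the baseline assessment, so this is an upper scenario, and it concerns a secondary outcome.
- *The 74%, 90% and 97% are error rates of the plan.* They are so only if any positive mean counts as a trend, a rule the documents do not state. At the plan's alpha of 0.05 the figures are 9%, 23% and 46%.

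**Conclusion.** The mismatch is in the text and should be corrected. Hypothesis 2 as worded has no control, no threshold and no corresponding analysis, while the planned controlled test answers a question that no hypothesis asks.

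With zero program effect, an assumed upward drift of 0.1 to 0.3 SD would produce a significant before-after improvement in about 9% to 46% of trials, against about 2.5% for the randomised contrast. The contradiction between the sections does not depend on any assumption. The sizes depend on the assumed drift, normal changes and 20 completers per group; the claim that the randomised contrast is protected also assumes that dropout does not differ by group in a way related to outcome. The direction of drift is unknown, so the before-after reading could mislead either way.

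The planned safeguard is least secure for the primary outcome, because the listed ActiGraph schedule gives GROUP2 no baseline step count.

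**What to change.** 1. Restate Hypothesis 2 as the GROUP1 versus GROUP2 difference in change from baseline to week 12, with 7-day step count primary, reported as an estimate with a 95% CI.
2. Reword the Section G sentence, which attaches the change to participants assigned to the intervention and then compares it between groups. It should name the change in both groups.
3. Keep the pooled start-to-end change for SD estimation. Where it is shown as response, label it uncontrolled and present it by group.
4. Reconcile the ActiGraph schedule with the baseline collection in Sections I and D and with the test in Section G. If GROUP2 has no baseline wear, state that step count cannot support the change contrast and compare the groups' week-12 step counts instead.

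Items 1 to 3 are wording only. Item 4 is wording if GROUP2 baseline wear is already intended; otherwise it means one added wear period for 25 participants or the week-12 comparison. The scientific cost is that the controlled contrast rests on about 20 completers per group, has a CI half-width of about 0.64 SD, and is less likely to look favourable than the before-after change.
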